## **12.8 Evaluation of Response**

Tumor response assessment will be based on treating investigator assessment and institutional standard of care and this assessment will be captured in this study.

# **13. REGISTRATION PROCESS**

## **13.1 CTEP Registration Procedures**

Food and Drug Administration (FDA) regulations and National Cancer Institute (NCI) policy require all individuals contributing to NCI-sponsored trials to register and to renew their registration annually. To register, all individuals must obtain a Cancer Therapy Evaluation Program (CTEP) Identity and Access Management (IAM) account at <https://ctepcore.nci.nih.gov/iam>. In addition, persons with a registration type of Investigator (IVR), Non-Physician Investigator (NPIVR), or Associate Plus (AP) (i.e., clinical site

staff requiring write access to OPEN, Rave, or acting as a primary site contact) must complete their annual registration using CTEP's web-based Registration and Credential Repository (RCR) at <https://ctepcore.nci.nih.gov/rcr>.

RCR utilizes five person registration types.

- IVR — MD, DO, or international equivalent;
- NPIVR — advanced practice providers (e.g., NP or PA) or graduate level researchers (e.g., PhD);
- AP — clinical site staff (e.g., RN or CRA) with data entry access to CTSU applications (e.g., Roster Update Management System (RUMS), OPEN, Rave,);
- Associate (A) — other clinical site staff involved in the conduct of NCI-sponsored trials; and
- Associate Basic (AB) — individuals (e.g., pharmaceutical company employees) with limited access to NCI-supported systems.

RCR requires the following registration documents:

Documentation Required	IVR	NPIVR	AP	A	AB
FDA Form 1572	✓	✓			
Financial Disclosure Form	✓	✓	✓		
NCI Biosketch (education, training, employment, license, and certification)	✓	✓	✓		
GCP training	✓	✓	✓		
Agent Shipment Form (if applicable)	✓				
CV (optional)	✓	✓	✓		

An active CTEP-IAM user account and appropriate RCR registration is required to access all CTEP and CTSU (Cancer Trials Support Unit) websites and applications. In addition, IVRs and NPIVRs must list all clinical practice sites and Institutional Review Boards (IRBs) covering their practice sites on the FDA Form 1572 in RCR to allow the following:

- Addition to a site roster;
- Assign the treating, credit, consenting, or drug shipment (IVR only) tasks in OPEN;
- Act as the site-protocol Principal Investigator (PI) on the IRB approval; and
- Assign the Clinical Investigator (CI) role on the Delegation of Tasks Log (DTL).

In addition, all investigators act as the Site-Protocol PI, consenting/treating/drug shipment, or as the CI on the DTL must be rostered at the enrolling site with a participating organization (i.e., Alliance).

Additional information can be found on the CTEP website at

<https://ctep.cancer.gov/investigatorResources/default.htm>. For questions, please contact the **RCR Help Desk** by email at [[contact]](mailto:[contact]).

## 13.2 Cancer Trials Support Unit (CTSU) Registration Procedures

This study is supported by the NCI Cancer Trials Support Unit (CTSU).

Protocol documents are found on the CTSU website, but supplemental documents may be available on the Wake Forest NCORP Research Base website (<https://wakencorp.phs.wakehealth.edu/dspLogin.cfm>). Permission to view and download the neurocognitive test packet are restricted and is based on person specific training and is housed on the Wake Forest NCORP Research Base website.

### IRB Approval

For CTEP and Division of Cancer Prevention (DCP) studies open to the National Clinical Trials Network (NCTN) and NCI Community Oncology Research Program (NCORP) Research Bases after March 1, 2019, all U.S.-based sites must be members of the NCI Central Institutional Review Board (NCI CIRB). In addition, U.S.-based sites must accept the NCI CIRB review to activate new studies at the site after March 1, 2019. Local IRB review will continue to be accepted for studies that are not reviewed by the CIRB, or if the study was previously open at the site under the local IRB. International sites should continue to submit Research Ethics Board (REB) approval to the CTSU Regulatory Office following country-specific regulations.

Sites participating with the NCI CIRB must submit the Study Specific Worksheet (SSW) for Local Context to the CIRB using IRBManager to indicate their intent to open the study locally. The NCI CIRB's approval of the SSW is automatically communicated to the CTSU Regulatory Office, but sites are required to contact the CTSU Regulatory Office at [[contact]](mailto:[contact]) to establish site preferences for applying NCI CIRB approvals across their Signatory Network. Site preferences can be set at the network or protocol level. Questions about establishing site preferences can be addressed to the CTSU Regulatory Office by emailing the email address above or calling [name].

In addition, the Site-Protocol Principal Investigator (PI) (i.e. the investigator on the IRB/REB approval) must meet the following criteria to complete processing of the IRB/REB approval record:

- Holds an Active CTEP status;
- Active status at the site(s) on the IRB/REB approval on at least one participating organization's roster;
- If using NCI CIRB, active on the NCI CIRB roster under the applicable CIRB Signatory Institution(s) record;
- Includes the IRB number of the IRB providing approval in the Form FDA 1572 in the RCR profile;
- Lists all sites on the IRB/REB approval as Practice Sites in the Form FDA 1572 in the RCR profile; and
- Holds the appropriate CTEP registration type for the protocol.

### Additional Requirements

Additional site requirements to obtain an approved site registration status include:

- An active Federal Wide Assurance (FWA) number;

- An active roster affiliation with the Lead Protocol Organization (LPO) or a Participating Organization (PO);
- An active roster affiliation with the NCI CIRB roster under at least once CIRB Signatory Institution (US sites only); and
- Compliance with all protocol-specific requirements (PSRs).

### **Protocol Specific Requirements for WF-1801 Site Registration**

Upon site registration approval in RSS, the enrolling site may access OPEN to complete enrollments. The enrolling site will select their credentialed provider treating the subject in the OPEN credentialing screen, and may need to answer additional questions related to treatment in the eligibility checklist.

- Neurocognitive training and certification through Wake Forest NCORP Research Base is required prior to participants being enrolled. At least one staff member per site must be certified.
- Site Open to Enrollment (SOTE) letter from WF NCORP RB, which is provided to the site once all site start-up activities have been completed.

### **Submitting Regulatory Documents:**

Submit required forms and documents to the CTSU Regulatory Office via the Regulatory Submission Portal on the CTSU members' website.

To access the Regulatory Submission Portal log on to the CTSU members' website, go to the *Regulatory* section and select *Regulatory Submission*.

Institutions with patients waiting that are unable to use the Regulatory Submission Portal should alert the CTSU Regulatory Office immediately by phone or email: [name] or [[contact]](mailto:[contact]) in order to receive further instruction and support.

### **Checking Site's Registration Status:**

Site registration status may be verified on the CTSU members' website.

- Click on *Regulatory* at the top of the screen;
- Click on *Site Registration*; and
- Enter the site's 5-character CTEP Institution Code and click on Go:
  - Additional filters are available to sort by Protocol, Registration Status, Protocol Status, and/or IRB Type.

Note: The status shown only reflects institutional compliance with site registration requirements as outlined above. It does not reflect compliance with protocol requirements for individuals participating on the protocol or the enrolling investigator's status with the NCI or their affiliated networks.

### 13.3 Patient Enrollment

The Oncology Patient Enrollment Network (OPEN) is a web-based registration system available on a 24/7 basis. OPEN is integrated with CTSU regulatory and roster data and with the Lead Protocol Organization (LPOs) registration/randomization systems or Theradex Interactive Web Response System (IWRS) for retrieval of patient registration/randomization assignment. OPEN will populate the patient enrollment data in WF NCORP RB's clinical data management system, REDCap.

Requirements for OPEN access:

- A valid CTEP-IAM account;
- To perform enrollments or request slot reservations: Be on a LPO roster, ETCTN Corresponding roster, or PO roster with the role of Registrar. Registrars must hold a minimum of an AP registration type;
- If a Delegation of Tasks Log (DTL) is required for the study, the registrar(s) must hold the OPEN Registrar task on the DTL for the site; and
- Have an approved site registration for a protocol prior to patient enrollment.

To assign an Investigator (IVR) or Non-Physician Investigator (NPIVR) as the treating, crediting, consenting, drug shipment (IVR only), or receiving investigator for a patient transfer in OPEN, the IVR or NPIVR must list the IRB number used on the site's IRB approval on their Form FDA 1572 in RCR. If a DTL is required for the study, the IVR or NPIVR must be assigned the appropriate OPEN-related tasks on the DTL.

Prior to accessing OPEN, site staff should verify the following:

- Patient has met all eligibility criteria within the protocol stated timeframes; and
- All patients have signed an appropriate consent form and Health Insurance Portability and Accountability Act (HIPAA) authorization form (if applicable).

Note: The OPEN system will provide the site with a printable confirmation of registration and treatment information. Please print this confirmation for your records.

Access OPEN at <https://open.ctsu.org> or from the OPEN link on the CTSU members' website. Further instructional information is in the OPEN section of the CTSU website at <https://www.ctsu.org> or <https://open.ctsu.org>. For any additional questions, contact the CTSU Help Desk at [name] or [[contact]](mailto:[contact]).

### 13.4 Data Submission / Data Reporting

REDCap is a clinical data management system being used for data collection for this trial/study. Access to the trial in REDCap is granted through the Wake Forest NCORP Research Base. To access REDCap:

- Site staff will need to be registered with CTEP and have a valid and active CTEP-IAM account; and
- Must have a minimum of an AP registration type.
- Must be on the Wake Forest NCORP Research Base roster in NCORP-SYS for active study sites.

Refer to <https://ctep.cancer.gov/investigatorResources/default.htm> for registration types and documentation required.

Upon initial site registration approval for the study in Regulatory Support System (RSS), all persons on the Study Site Role form in the Study Start-up Packet needing database access will be sent a study invitation e-mail from REDCap with their username and password. Please note, site users will not be able to access the study in REDCap until all required study specific trainings are completed.

Further instructional information will be provided after CTSU site approval is received and the site initiation packet is completed and returned to [[contact]](mailto:[contact]). For any additional questions on REDCap contact the Wake Forest NCORP Research Base at [contact] or [[contact]](mailto:[contact]).

**APPENDIX A****Performance Status Criteria****ECOG Performance Status Scale**

Grade	Descriptions
0	Normal activity. Fully active, able to carry on all pre-disease performance without restriction.
1	Symptoms, but ambulatory. Restricted in physically strenuous activity, but ambulatory and able to carry out work of a light or sedentary nature ( e.g. , light housework, office work).
2	In bed <50% of the time. Ambulatory and capable of all self-care, but unable to carry out any work activities. Up and about more than 50% of waking hours.
3	In bed >50% of the time. Capable of only limited self-care, confined to bed or chair more than 50% of waking hours.
4	100% bedridden. Completely disabled. Cannot carry on any self-care. Totally confined to bed or chair.
5	Dead.

## APPENDIX B

### Data Submission Checklist

WF NCORP Research Base #1801 Ramipril	Site CTEP ID: _____ Staff Filling Out Form (initials): _____	PID: _____ Patient Initials: _____ Date (mm/dd/yyyy): _____
--	--	---

 Enrollment	Date Submitted
Eligibility/Enrollment in OPEN	
Patient Demographics/Health Behavior	
Signed Informed Consent	

 Baseline	Date Submitted
Baseline Data Collection Form	
NeuroCog & PROs booklet	
MRI report	
DNA (APOE genotype) Form	

 Week 1 - Titration	Date Submitted
Ramipril Titration Form – Week 1	
Ramipril Medication Diary, if end of month	
Submit any AE/SAEs per protocol	

 Week 2 - Titration	Date Submitted
Ramipril Titration Form – Week 2	
Ramipril Medication Diary, if end of month	
Submit any AE/SAEs per protocol	

 Week 3 - Titration	Date Submitted
Ramipril Titration Form – Week 3	
Ramipril Medication Diary , if end of month	
Submit any AE/SAEs per protocol	

 Week 4	Date Submitted
Ramipril Administration Form - Week 4	
Ramipril Medication Diary, if end of month	
Submit any AE/SAEs per protocol	

WF NCORP Research Base #1801 Ramipril	Site CTEP ID: _____ Staff Filling Out Form (initials): _____	PID: _____ Patient Initials: _____ Date (mm/dd/yyyy): _____
--	--	---

 Week 5	Date Submitted
Ramipril Administration Form – Week 5	
Ramipril Medication Diary, if end of month	
Submit any AE/SAEs per protocol	

 Week 6	Date Submitted
Ramipril Administration Form – Week 6	
NeuroCog & PROs booklet for week 6 - RT completion	
Ramipril Medication Diary, if end of month	
Submit any AE/SAEs per protocol	

 Week 10 (1 Month Post RT)	Date Submitted
Ramipril Admin. Assessment Form – Wk 10	
NeuroCog & PROs booklet for week 10	
MRI report	
Ramipril Medication Diary	
Submit any AE/SAEs per protocol	

 Week 14 (2 Month Post RT) – Telephone call	Date Submitted
Ramipril Admin. Assessment Form – Wk 14	
Ramipril Medication Diary	
Submit any AE/SAEs per protocol	

 Week 18 (3 Month Post RT) – Telephone call	Date Submitted
Ramipril Admin. Assessment Form – Wk 18	
Ramipril Medication Diary	
Submit any AE/SAEs per protocol	

 Week 22 (4 Month Post RT)	Date Submitted
Ramipril Admin. Assessment Form – Wk 22	
NeuroCog & PROs booklet for week 22	
MRI report	
Ramipril Medication Diary	
Submit any AE/SAEs per protocol	

WF NCORP Research Base #1801 Ramipril	Site CTEP ID: _____ Staff Filling Out Form (initials): _____	PID: _____ Patient Initials: _____ Date (mm/dd/yyyy): _____
--	--	---

 Week 26 (5 Month Post RT)	Date Submitted
Ramipril Phone F/U Form – Week 26	
Submit any AE/SAEs per protocol	
OFF-STUDY Form	

**Other Forms:**

- **Screening Logs** should be submitted at the end of each month. Sites should keep the original screening logs as source documents. (see Appendix C)
- **Adverse Event Form** should be used for adverse event reporting via REDCap and per protocol when needed.
- **Monthly Patient Ramipril Medication Diary** can be found in Appendix D of the protocol. Sites will transfer the information into REDCap for each diary. All diaries are considered source documents and should be kept by the site.
- **DNA (APOE genotype)** for blood collection submission and kits requests can be found in Appendix E of the protocol.

Reason	Race	Ethnicity	Gender	Sex
1. Investigator decision – [be specific]	American Indian or Alaska Native	Hispanic or Latino	Female Gender	Male
2. Ineligible – [Why, be specific?]	Asian	Not Hispanic or Latino	Male Gender	Female
3. Participant decision - Transportation	Black or African American	Not reported	Unknown	Unknown
4. Participant decision – Time Involvement	Native Hawaiian or other Pacific Islander	Unknown		
5. Participant decision – Overwhelmed	White			
6. Participant decision – Did not like the study assessments/questionnaires	Not Reported			
7. Participant decision – Did not want to take Ramipril	Unknown			
8. Participant decision – Study too confusing				
9. Participant decision – Does not like research				
10. Participant decision -too sick or ill				
11. Participant decision -Desires compensation				
12. Participant decision -Other [be specific]				
13. Other [be specific]				

## APPENDIX D

**Monthly Patient Ramipril Medication Diary****Instructions:** Use this calendar to record the number of pills that you take each day and as a reminder to take your medication.

Be sure to bring this calendar and your pill bottle with you for all return appointments.

**Please use only one calendar per month**Patient Initials  ,   Last, First Middle Jan Feb Mar Apr May June July Aug Sept Oct Nov Dec Year: 20 \_\_\_\_

Day of Week	Day of Week	Day of Week	Day of Week	Day of Week	Day of Week	Day of Week	Day of Week
 # of pills taken ____	 # of pills taken ____	 # of pills taken ____	 # of pills taken ____	 # of pills taken ____	 # of pills taken ____	 # of pills taken ____	 # of pills taken ____
 # of pills taken ____	 # of pills taken ____	 # of pills taken ____	 # of pills taken ____	 # of pills taken ____	 # of pills taken ____	 # of pills taken ____	 # of pills taken ____
 # of pills taken ____	 # of pills taken ____	 # of pills taken ____	 # of pills taken ____	 # of pills taken ____	 # of pills taken ____	 # of pills taken ____	 # of pills taken ____
 # of pills taken ____	 # of pills taken ____	 # of pills taken ____	 # of pills taken ____	 # of pills taken ____	 # of pills taken ____	 # of pills taken ____	 # of pills taken ____
 # of pills taken ____	 # of pills taken ____	 # of pills taken ____	 # of pills taken ____	 # of pills taken ____	 # of pills taken ____	 # of pills taken ____	 # of pills taken ____
 # of pills taken ____	 # of pills taken ____	 # of pills taken ____	 # of pills taken ____	 # of pills taken ____	 # of pills taken ____	 # of pills taken ____	 # of pills taken ____

Comments: \_\_\_\_\_

Patient Signature \_\_\_\_\_

Date \_\_\_\_\_

For Office Use Only:
Research Base Patient ID: _____
Site Name: _____

WF NCORP Research Base WF-1801 Ramipril
--

**Administration schedule for study medication (Ramipril)**

\_\_\_\_ Week 1- take **one** 1.25 mg capsules of Ramipril by mouth per day.  
Month/Date

\_\_\_\_ Week 2- take **two** 1.25 mg capsules of Ramipril (2.5 mg total) by mouth per day.  
Month/Date

\_\_\_\_ Week 3- take **four** 1.25 mg capsules of Ramipril (5 mg total) by mouth per day.  
Month/Date

\_\_\_\_ Week 4- take \_\_\_\_ 1.25 mg capsules of Ramipril by mouth per day and continue for  
Month/Date 4 months after completion of radiation.

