### **5.1.2 Ramipril**

Ramipril (e.g. Altace® or Tritace®) is an ACE-I. It is currently FDA approved for use in the treatment of hypertension and for reducing the risk of myocardial infarction, stroke and death from cardiovascular causes.

Study intervention (Ramipril) will be administered on an outpatient basis. Reported AEs and potential risks are described in Section 6.2.

- Ramipril will be taken once daily by mouth

- Weeks 1-3 titration of Ramipril during RT
  - weekly titration from 1.25 mg x 7 days, 2.5 mg x 7 days, then 5 mg x 7 days,
  - titration to highest tolerable dose of at least 2.5 mg daily
- Weeks 4-6 until 4 months post RT
  - highest tolerable dose of at least 2.5 mg daily.
  - highest allowable dose of Ramipril for this study will be 5 mg daily.

Current Ramipril dose should be continued until local institutional lab or research LabCorp lab results are received, which should be used to evaluate toxicities during Weeks 1-6 of RT (see Section 5.2 for further guidance). During Weeks 1-6 of RT, LabCorp and/or local institutional labs should be drawn only after  $\geq 4$  doses of current Ramipril dose have been taken by the patient. If local institutional labs are going to be used for toxicity assessments, please use them for all Week 1-6 visits for consistency and also draw research LabCorp labs to allow for comparison of

labs across sites. At 1 month post-RT, standard of care local institutional labs will be used to evaluate toxicities per protocol. In the event of inability to obtain LabCorp results in an appropriate time interval, local standard of care labs can be used for Ramipril titration decision making and other protocol related activities.

If lab abnormalities are detected that would affect the conduct of the study, treating physicians should consider whether correctable disease or treatment related toxicities (e.g. dehydration, nausea and vomiting, etc.) could be responsible. If so, clinicians should attempt to address those issues and repeat the labs within 24-48 hours for protocol decision making.

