## 5.2 Ramipril Administration

- Drug will be self-administered orally on an outpatient basis. Ramipril should be taken before bedtime, with or without food.
- Titration of Ramipril will be performed by the local investigator. The medication will be titrated to tolerance and taken each evening during the course of RT (starting on the first day +/- 3 days) and continued for an additional four months after completion of RT.
  - If patients are taking pre-existing anti-hypertensive medications, the treating oncologist (possibly in conjunction with the patient's primary care physician) may modify the pre-existing anti-hypertensive regimen if there is a concern that the addition or titration of Ramipril may lead to hypotension.
  - Blood pressure and blood chemistry (creatinine, potassium, and GFR) will be checked weekly during titration period prior to titrating to the next dose. Ramipril dose will not be increased any further during titration if any of the following conditions are met:
    - systolic blood pressure is less than 100 mm Hg,
    - serum creatinine increases to above the upper limit of normal of either the local institutional lab or LabCorp (LabCorp normal creatinine value range is 0.76-1.27), or if the creatinine remains below the upper limit of normal but has increased  $\geq$  to 100% of the previous week's value from the same lab.
      - If an institutional creatinine result is used to guide Ramipril titration then the upper limit of normal of the institutional lab should be used to guide titration as described above.
      - Either the local institutional lab or LabCorp lab should be chosen and used for all Week 1-6 visits to be consistent with the normal values

used during the titration period. However, if in the event of inability to obtain LabCorp results in an appropriate time interval, local standard of care labs can be used for Ramipril titration decision making and other protocol related activities.

- If choosing to use local institutional labs for Week 1-6 visits, please also draw and submit research LabCorp labs to allow for comparison across study sites.
  - serum potassium rises above 5.0 mEq/L,
  - Grade 3 or greater toxicity attributable to drug is identified during weekly toxicity evaluation.

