- Following lack of significant toxicity (including laboratory and blood pressure) review after week 1, patients will take two 1.25 mg capsules of Ramipril (2.5 mg total) per day. Following lack of significant toxicity review after week 2, patients will take four 1.25 mg capsules (5 mg total) per day. The titration of the medication is expected to be complete within the first 3-4 weeks of RT and the Ramipril will continue at the same dose during the remainder of RT and for an additional four months after RT.
- Ramipril treatment may be terminated early if intercurrent illness occurs that prevents further administration, unacceptable adverse events occur, the patient decides to withdraw from the study or if changes in the patient's condition occur to render the patient unacceptable for further treatment in the judgment of the investigator. Refer to Section 8.3 Off-Agent for guidelines.
- Delays in radiation therapy will not affect Ramipril dose titration. If radiotherapy is delayed, the patient will continue on their current dose of Ramipril, or the dose of Ramipril could be reduced as per the above criteria if a significant toxicity occurred. If there is a delay in radiotherapy, patient would still continue Ramipril until 4-months post RT, which could mean the study visits may be pushed out the number of days of the delay. For example, if there is a 1 week RT delay, the patient would have the 1 month-Post RT visit at Week 11, instead of Week 10. A final toxicity assessment will be done by phone at 5 months post RT (Week 26).

If the patient misses a dose of study medication and if it is less than 4 hours late, have them take that dose of study medication as directed. If the patient misses a dose of study medication and if it is greater than 4 hours, do not have them take this dose. Have them take their regular dose at the usual time the following day. If more than one day is missed of study medication, please have them continue as soon as possible. Any missed doses of study medication should be documented on their patient diary.

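### The patient diary in Appendix D prints the Week 2 and Week 3 ramipril doses without condition, although the protocol allows each increase only after a clean weekly review.

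*Combined protocol and SAP*

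**What the plan says.** Section 5.2 makes both steps of the titration conditional. For the first: "Following lack of significant toxicity (including laboratory and blood pressure) review after week 1, patients will take two 1.25 mg capsules of Ramipril". For the second: "Following lack of significant toxicity review after week 2, patients will take four 1.25 mg capsules (5 mg total) per day". Blood pressure, creatinine, potassium and GFR are checked each week before the next step. The hold rule reads "Ramipril dose will not be increased any further during titration if any of the following conditions are met", and the conditions are systolic pressure below 100 mm Hg, a creatinine criterion, potassium above 5.0 mEq/L, and attributable toxicity of Grade 3 or worse. Section 5.1.2 adds a rule for pending results: "Current Ramipril dose should be continued until local institutional lab or research LabCorp lab results are received". It aims for the "highest tolerable dose of at least 2.5 mg daily", so 2.5 mg is a permitted final dose and not every patient reaches 5 mg.

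Appendix D gives the patient a four-line schedule:

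- Week 1: one capsule.
- Week 2: two capsules.
- Week 3: four "1.25 mg capsules of Ramipril (5 mg total) by mouth per day".
- Week 4: a blank, followed by "1.25 mg capsules of Ramipril by mouth per day and continue for" four months after radiation.

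Each line has an unlabelled Month/Date blank beside it. The rest of the diary covers missed doses, medicines to avoid, side effects and when to call. It does not tell the patient to wait for clearance before increasing.

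**The concern.** The diary is the written dosing instruction that the patient takes home, and the hold rules sit in a document the patient does not have. When a hold applies, the two give different doses. Keeping the patient on the lower dose then depends on staff correcting or overriding a printed count. The matter is patient safety: the conditions that trigger a hold are low blood pressure, renal function, potassium and severe toxicity, and Section 6.1 names hypotension (11%) as the major risk of ramipril in people without hypertension.

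The form itself treats the dose as individual only from Week 4, where it leaves the count blank. Under Sections 5.1.2 and 5.2 the dose is already individual from Week 2.

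**Working it through.** **Inputs.** Capsule strength 1.25 mg and printed counts 1, 2 and 4 for Weeks 1 to 3 (Appendix D); seven days per step and 5 mg maximum (Section 5.1.2); 133 capsules in the first bottle, meant to cover Weeks 1 to 6 (Section 6.6).

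**The plan's own figure.** The bottle size reproduces from the schedule with no hold: 7 × 1 + 7 × 2 + 28 × 4 = 7 + 14 + 112 = 133.

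**Dose stated against dose permitted.** Ratio = printed dose / permitted dose. Excess over a full step = 7 × (printed count − permitted count) capsules, times 1.25 mg.

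| Patient's state | Printed | Permitted | Ratio | Excess over 7 days |
|---|---|---|---|---|
| Week 2, held at one capsule | 2.5 mg | 1.25 mg | 2 | 7 × (2 − 1) = 7 capsules, 8.75 mg |
| Week 3, held at two capsules | 5 mg | 2.5 mg | 2 | 7 × (4 − 2) = 14 capsules, 17.5 mg |
| Week 3, still held at one capsule | 5 mg | 1.25 mg | 4 | 7 × (4 − 1) = 21 capsules, 26.25 mg |

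The last row arises if a patient is held at both reviews. It also arises after one hold, if the rule is read as stopping all further increases once a condition is met. The protocol does not clearly say what happens to a patient left at 1.25 mg, since its target is at least 2.5 mg.

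**Does supply prevent the error?** No. The printed schedule through Week 3 uses 7 + 14 + 28 = 49 capsules, leaving 133 − 49 = 84. A patient held at 2.5 mg from Week 2 needs 7 + 35 × 2 = 77 over six weeks; one kept at 1.25 mg needs 42. Both have the extra capsules at home.

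**Are held or pending patients foreseeable?** Yes, from the protocol's own terms:

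- Labs are drawn only after at least four doses at the current level (Section 5.1.2), and dosing is in the evening (Section 5.2). By inference, the earliest draw is about day 5, while the printed Week 2 dose falls on day 8. That leaves about three days for draw, result and review.
- Visits in Weeks 1 to 3 have a window of ±3 days (Section 7.2), so a review within window can come after the printed step is due.
- Section 5.1.2 provides for late LabCorp results and for repeat labs within 24 to 48 hours.
- Section 5.2 expects titration to take three to four weeks. The sheet prints a three-week course.
- Entry limits lie close to the hold limits. Systolic pressure: 110 mm Hg or more at entry, hold below 100. Potassium: below 5.0 mEq/L at entry, hold above 5.0. Creatinine: up to 1.7 mg/dl is eligible, while the LabCorp upper limit used for holds is 1.27.

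The documents give no rate for the hold conditions or for patient error, so the number of patients affected cannot be estimated.

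**The case against.** The best defence is that Appendix D repeats the default regimen, which Section 5.1.2 itself lists as a plain weekly sequence, and that the governing rules address the professional in charge: "Titration of Ramipril will be performed by the local investigator". On that reading the sheet is a summary without a caveat and not a second dosing rule. Staff could leave a line's Month/Date blank empty until the patient is cleared. Patients are reviewed weekly, a Ramipril Titration Form is completed in each of Weeks 1 to 3 (Appendix B), diaries come back weekly during radiotherapy (Sections 5.6.2 and 7.3), and patients attend for radiation five days a week (Section 5.1.1.2). Local labs may replace late LabCorp results. Section 6.2.1 reports generally mild side effects in hypertension trials, unrelated to dose from 1.25 to 20 mg. The consent form and the titration form are not in the text reviewed and may tell the patient to wait.

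Most of this stands as mitigation. It lowers the chance of error and makes the seven-day figures upper bounds. It does not remove the conflict. The patient holds the sheet and not Section 5.2. The Month/Date blank is not described as an authorisation, appears equally on the Week 1 line that needs no clearance, and can delay a step but cannot state a held dose. Returned diaries may show a wrong dose only after it has been taken. What other patient materials say is unknown, and a correct statement there would still contradict this sheet.

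**Conclusion.** The concern holds. As written, Appendix D gives a held or pending patient a dose that Sections 5.1.2 and 5.2 do not permit: twice the permitted dose at the next step, and four times in the worst case. The excess figures assume that the patient follows the sheet for a whole seven-day step and that no one intervenes.

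The clinical weight is modest because the sheet stays within 5 mg and several controls operate around it. It should nevertheless be corrected, because it is a wrong dosing instruction in a patient's hands and it conflicts with a safety rule.

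**What to change.** In Appendix D, do one of the following:

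- Leave the Week 2 and Week 3 capsule counts blank, as on the Week 4 line, for the site to fill in and date after that week's review.
- Keep the printed counts and add to each of the two lines: *only after your study team confirms; until then stay on your current number of capsules*.

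Blank counts can state a held dose exactly, at the price of two handwritten numbers per patient and some risk of writing errors. The added sentence avoids that risk. Either change is one revision of a patient form. Because the form is an appendix to the protocol, the revision would pass through the amendment approvals named in Section 11.5. The dosing plan, sample size and analysis are unaffected.
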